5.1.7. Treatment Failure Rules

NA

5.1.8. Missing Data Imputation

Data of study endpoints from subjects who started a protocol-prohibited medication/therapy during the study period that could improve psoriasis will be set to 'missing' from that point onward. The protocol-prohibited medications/therapies are listed in section 8.1 of the CSP. For the statistical analysis of Study Part 3, protocol prohibited medication/therapy will be identified in the SDTM DV domain as DVDECOD='RECEIVED DISALLOWED CONCOMITANT TREATMENT'.

After the rule for handling of protocol-prohibited medication/therapy is applied, missing data will be handled as follows:

- Non-responder imputation for binary efficacy endpoints will be applied for subjects with missing data at any study visit.
- Last Observation Carried Forward (LOCF) imputation for continuous efficacy endpoints will be applied for subjects with missing data in Study Part 3.
 - This approach implies that a separate "endpoint" visit will be calculated that gets the imputed value, thus leaving the observed value as it is, if data are summarized descriptively only.
 - The earliest visit used for LOCF approach is the week 68 visit; no data from Parts 1 and 2 will be used as LOCF value for the week 116/164/220 visit.

- Time-to-event analyses of binary endpoints will be performed after the rule for handling of protocol-prohibited medication/therapy is applied (missing data will not be replaced for time-to-event analyses).

An 'observed cases analysis' for all binary and continuous endpoints in Study Part 3 without any imputation of missing data (ie, also not set to missing once protocol-prohibited medication/therapy is started) will also be done. These analyses will provide only descriptive statistical results and will also include by-visit data of Study Parts 1 and 2 (see section 5.6).

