Precaution: for those who may carry a higher risk for severe COVID-19 illness (eg, those aged over 65 years), follow guidance from local health authorities when weighing the potential benefits and risks of enrolling in the study, and during study participation

NOTES:

Investigators should ensure that all study enrollment criteria have been met at baseline. If a subject's clinical status changes (including any available laboratory results or receipt of additional medical records) before the first dose of study drug is given such that he or she no longer meets all eligibility criteria, then the subject should be excluded from participation in the study.

Prior to randomization at week 28 and again prior to entering Study Part 3 at week 68 exclusion criterion 1 (subject has a clinically active psoriasis arthritis which needs systemic therapy beyond NSAIDs) has to be re-evaluated and subjects with diagnosed PsA who need systemic therapy beyond NSAIDs are to be excluded from further participation in the trial.

SRe who already had their regular final study visit at week 116 before Study Amendment 5 was implemented and have not yet completed the study for more than 12 weeks, will be asked by the investigator if they want to participate in the long-term extension (LTE) follow-up phase defined by Amendment 5. All SRe with PASI ≤ 5 at week 116 are allowed to enter LTE with the first visit in week 128 (12 weeks after last study visit). In case of PASI > 5 at week 128, it will be possible to start re-treatment according to protocol. Subjects who have previously used an antipsoriatic medication prohibited by the protocol are not allowed to continue after week 116.

Section 17.4 describes the required documentation to support meeting the enrollment criteria.

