1. INTRODUCTION

The statistical analysis plan (SAP) is a detailed technical extension to the Clinical Study Protocol (CSP) and follows the principles of the guideline ICH E9.

Statistical analyses of Janssen-Cilag GmbH CSP CNTO1959PSO3012 are performed for each of the three Study Parts (of which Parts 1 and 2 are already completed):

- The exploratory analysis of Study Part 1 (“Open-label treatment phase”) occurred after all subjects had completed their visit at week 28 (ie, 28 weeks after study inclusion) or discontinued earlier. This analysis included the safety analysis and all efficacy measures until the week 28 visit.
- The confirmatory analysis of this study was performed at the end of Study Part 2 (“Double-blind treatment phase”), ie, after all subjects had completed their visit at week 68 (ie, 40 weeks after randomization) or discontinued earlier. This analysis included the confirmatory analysis of the primary endpoint, and the exploratory analyses of the major secondary endpoints and all other predefined efficacy and safety analyses from week 28 until week 68).

The analyses of Study Part 3 (“Drug withdrawal phase”) will be exploratory and will occur after all subjects have completed, if not gone into re-treatment before, their visit at week 116 (ie, 48 weeks after inclusion in Study Part 3 at week 68), at week 164 (ie, 96 weeks after inclusion in Study Part 3 at week 68), and at week 220 (ie, 152 weeks after inclusion in Study Part 3 at week 68). Only subjects who started Study Part 3 in study groups 3a or 3b will be included in the analyses. These analyses will include the safety evaluations and all efficacy measures after week 68 and will cover the time until week 116/164/220, respectively. Thus, the statistical analysis for Study Part 3 will consist of two interim analyses and one final analysis. All three analyses are described in the current SAP.

Final decisions about which subjects are to be included in the analyses of the Study Parts 1, 2, or 3, are made during the Data Review or Dry Run Meetings.

This current SAP describes the statistical analyses planned to be performed for Study Part 3 and should be read in conjunction with the CSP and the electronic Case Report Form (eCRF). Statistical analyses of study data recorded before week 68 have been specified in separate SAPs, if not otherwise specified.

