4.2.1. Intent-to-Treat Analysis Set (ITT)

For all efficacy analyses to compare study groups **3a** and **3b** in Study Part 3, all subjects entering Study Part 3 (either group 3a or 3b) will be included in the Intent-to-treat analysis set (ITT).

Note1: Subjects entering study group 3c, ie, the re-treatment arm, will be evaluated separately. Analysis is not covered by the present SAP.

Note 2: In the current SAP template the term 'full analysis set' is used. In this SAP the term 'intent-to-treat analysis set' is used instead to match the Clinical Study Protocol. In terms of content, there is no difference between the two names.

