5.2. Participant Dispositions

The number of subjects in the following disposition categories will be summarized throughout the study for Study Part 3 by study groups (ie, groups **3a**, **3b**) and the total of group **3a** and **3b**:

- Subjects who entered groups 3a or 3b of Study Part 3 (without those subjects who started re-treatment already at the week 68 visit)
- Subjects of groups 3a and 3b who completed Study Part 3 until the week 116/164/220 visit
- Subjects of groups 3a and 3b who discontinued Study Part 3 prematurely until the week 116/164/220 visit, respectively
- Subjects of groups 3a and 3b who started re-treatment at the week 116 visit
- Subjects of groups 3a and 3b who were still in the Withdrawal period at the week 116 visit
- Subjects of groups 3a and 3b who terminated Study Part 3 at the week 116 visit according to the unamended study protocol **
- Subjects of groups 3a and 3b who continued the Withdrawal phase beyond the week 116 visit
- Reasons for termination of study within Study Part 3 (subjects of groups 3a and 3b).

** For this subset of subjects, summary and frequency tables will be created showing age at baseline, sex, disease duration, as well as PASI and DLQI values at week 116.

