5.4.3. Analysis Methods

- Proportion of subjects who achieve an absolute PASI score of 0, ≤ 1 and <3 at weeks 116, 164, and 220
- Proportion of subjects who retain disease control from week 68 through week 116, from week 68 through week 164, and from week 68 through week 220

The proportion of subjects responding to treatment or maintaining disease control will be displayed in frequency tables providing the number and percentage of subjects per study group (NRI and OC analysis) along with odds ratio (OR), relative risk (RR) and risk difference (RD), and two-sided Wald-type 95% confidence intervals (95% CIs) stratified by 'disease duration'. For single proportions within each study group, unstratified two-sided 95% CIs according to Clopper-Pearson will be calculated. Graphical presentation will be presented by means of bar charts.

The two-group large-sample normal approximation Wald Z-test with Mantel-Haenszel stratum weights for 'disease duration' will be used to compare the respective proportion of subjects among the study groups. The Mantel-Haenszel estimate, the two-sided Wald-type 95% confidence limits, and the test for the difference of proportions will be computed by using Mantel-Haenszel stratum weights (Mantel & Haenszel, 1959) and the Sato variance estimator (Sato 1989).

The respective proportion of subjects will also be given by disease duration category (assessed at baseline, ie, ≤ 2 years, >2 years, and additionally only for ≤ 2 years: <15 months, 15 to 24 months) and overall, providing exploratory p-values (unadjusted Chi² test) for the difference between disease duration categories.

Details on handling of missing data are described in section 5.1.8. Subgroup analyses will be performed unstratified for the subgroups as specified in section 5.8.8.

Results will also be given for the entire population. In addition, in a modified OC analysis all subjects fulfilling the criteria for re-treatment within the week 116 visit window (ie, PASI>5) will be disregarded.

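### Read literally, non-responder imputation in Study Part 3 scores subjects whose planned study end was week 116 as failures at weeks 164 and 220, which can only lower those rates

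*SAP*

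**What the plan says.** **Analysis set.** Study Part 3 SAP 4.2.1: "all subjects entering Study Part 3 (either group 3a or 3b) will be included in the Intent-to-treat analysis set (ITT").

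**Imputation.** Study Part 3 SAP 5.1.8: "Non-responder imputation for binary efficacy endpoints will be applied for subjects with missing data at any study visit". No reason for missingness is exempted. Data after the start of prohibited therapy are set to missing first.

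**Who could continue after week 116.** Protocol 4.2 (Notes) concerns super-responders who had already had their regular final visit at week 116 when Amendment 5 was implemented. Those who "have not yet completed the study for more than 12 weeks, will be asked by the investigator if they want to participate" in the extension. A further sentence reads: "Subjects who have previously used an antipsoriatic medication prohibited by the protocol are not allowed to continue after week 116".

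**Recognition of the subset.** Study Part 3 SAP 5.2 has a separate disposition line for subjects who "terminated Study Part 3 at the week 116 visit according to the unamended study protocol". Its footnote adds: "For this subset of subjects, summary and frequency tables will be created showing age at baseline, sex, disease duration", together with PASI and DLQI at week 116.

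**General clause.** Study Part 3 SAP section 1: "Final decisions about which subjects are to be included in the analyses of the Study Parts 1, 2, or 3" are left to the Data Review or Dry Run Meetings.

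**Endpoints.** Study Part 3 SAP 5.4.3 analyses PASI 0, ≤1 and <3 at weeks 116, 164 and 220, and retained PASI <3 from week 68 through each of those weeks, by NRI and by observed cases (OC).

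**The concern.** NRI equates a missing value with failure. That is a routine, conservative choice when a subject drops out or stops for lack of effect. It fits poorly when a subject completed the study as then planned and was never offered a later visit. For a subject more than 12 weeks past week 116 when Amendment 5 was implemented, the missing week-164 and week-220 values follow from the enrolment date and say nothing about the skin. Such a subject could have PASI 0 at week 116 and still be scored as having lost control.

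The figures concerned are absolute rates of drug-free control at about two and three years after withdrawal, which are the time points that Amendment 5 added. They are major secondary endpoints, although exploratory. Results at weeks 68 and 116 are not touched.

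**Working it through.** **1. Is there an exemption elsewhere?** The places where one could stand are Study Part 3 SAP 5.1.8, 5.4.3, the final-analysis updates in 5.6 and 5.8.8, the change log in 6.2, and Protocol 11.11. None exempts these subjects or reduces the denominator for them.

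**2. Does another listed analysis give the same quantity without the problem?**
- *OC, single-visit endpoints.* Re-treated subjects are evaluated only up to R0. Section 5, Note 2 says this with reference to week 116; section 5.7, on safety, gives the same cut-off for weeks 164 and 220. Earlier failures therefore leave the denominator, and OC errs upward. Modified OC removes PASI >5 as well.
- *OC, retained control.* How earlier failures are treated is not defined.
- *Kaplan-Meier.* The finishers are censored, but the event is PASI >5 (5.5.1.1) or re-treatment (5.6), not loss of PASI <3.
- *LOCF or multiple imputation.* Protocol 11.11 permits both for binary endpoints, as options only. The Part 3 SAP lists LOCF for continuous endpoints and neither method for binary ones.

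**3. Counts.** The plan states no expected rate for these endpoints, so there is no figure of its own to reproduce except the re-treatment total. Inputs (Overall safety SAP 4.4 and 4.5): 273 entered withdrawal in 3a or 3b; 227 of them were re-treated for PASI >5 by week 220; 9 more were re-treated without a withdrawal phase; total 236.
- Check: 227 + 9 = 236, as stated.
- Never re-treated: 273 − 227 = 46, and 46/273 = 16.8%.

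The 227 cannot be week-220 responders. Responders and non-re-treated finishers therefore both lie within the 46.

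**4. Size.** Let k be the number of non-re-treated finishers who did not continue, and q the chance that such a subject would have responded. Neither is in the documents.
- Understatement = k × q / 273; one would-be responder is 1/273 = 0.37 points.
- Highest possible week-220 NRI rate = (46 − k)/273.

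| k (assumed) | ceiling, week 220 | understatement in points, q = 0.25 / 0.50 / 0.75 (assumed) |
|---|---|---|
| 5 | 41/273 = 15.0% | 0.5 / 0.9 / 1.4 |
| 10 | 36/273 = 13.2% | 0.9 / 1.8 / 2.7 |
| 20 | 26/273 = 9.5% | 1.8 / 3.7 / 5.5 |

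The understatement formula also holds at week 164 with its own q. The ceiling does not, because the number re-treated by week 164 is not given. For retained control, q = 0 for any finisher who had already shown PASI ≥3 after week 68.

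**5. Who was barred by date?** Those with week 0 earlier than implementation minus 128 weeks (116 + 12). Amendment 5 is dated 10 June 2021, and the start was planned for Q4 2018 (Protocol 3.1), so 1 October 2018 at the earliest.

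| implementation | barred if week 0 before | enrolment span from 1 Oct 2018 |
|---|---|---|
| 10 June 2021 (amendment date; lower bound) | 27 Dec 2018 | 87 days = 12.4 weeks |
| 10 Sept 2021 (assumed, 3 months) | 29 Mar 2019 | 179 days = 25.6 weeks |
| 10 Dec 2021 (assumed, 6 months) | 28 June 2019 | 270 days = 38.6 weeks |

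Visit windows of ±14 days shift these dates slightly. Protocol 17.1 requires ethics approval before implementation, so the first row is a floor and not a realistic case. These are spans of calendar time, not counts of subjects; a small k remains possible.

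**The case against.** *The outcome is not certain.* Weeks 164 and 220 were not scheduled visits for these subjects, section 5.2 lists them apart from premature discontinuations, and section 1 leaves inclusion to meetings. This stands as far as it goes: the documents do not prove that the finishers were imputed. But the rule as written covers them, the clause on meetings is general, and the recorded changes show no exemption.

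*Other imputations are foreseen.* Protocol 11.10 plans sensitivity analyses under different imputation rules, and 11.11 names LOCF for binary endpoints. LOCF would carry a finisher's week-116 PASI forward and keep a re-treated subject's PASI >5 as a failure. So a reader should not infer that the trial offers no route to a remedy. The route is optional, however, and the Part 3 SAP does not take it up.

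*The information is already planned.* Section 5.2 gives the count by study group and the week-116 PASI values. That stands, and it makes the remedy cheap. It does not connect these subjects with the week-164 and week-220 rates.

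*The size is unknown.* k and q are assumed throughout, the endpoints are exploratory with nominal p-values (5.1), and the shift is conservative. This stands, and it is why the point is minor.

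*It is too late to change the plan.* The Overall safety SAP (section 1) reports the Part 3 analyses as performed. This stands: anything added now is post hoc.

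**Conclusion.** The point holds as a minor one. Under the literal rule, finishers at week 116 who did not continue are non-responders at weeks 164 and 220, and the absolute NRI rates can only be too low, by 0.37 points for each one who would have responded. At week 220 this acts on a rate that cannot exceed 16.8% in any case. With k and q assumed as in the table, the understatement runs from about 0.5 to 5.5 points; with few finishers it is negligible.

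Two stronger readings are tempting. One is that the comparison of 3a with 3b, or of short with longer disease duration, is biased. The documents do not show this: the cut-off follows calendar date, the arms were randomized 1:1, and no count by arm or duration is given. The other is that the durability results are materially wrong. That would need the number of finishers, which the documents do not give. NRI itself is not at fault, and subjects barred from continuing because of prohibited medication are properly kept as failures.

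**What to change.** Keep the prespecified NRI. Label the following as post hoc.

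1. Beside the week-164 and week-220 NRI results, state how many finishers were imputed as non-responders, by study group and disease duration, with their week-116 PASI status from the 5.2 tables. Where possible, split them into barred by date, declined, and barred for prohibited medication.
2. Add one supplementary analysis:
   - *Retained control:* Kaplan-Meier for PASI <3, with failure at the first PASI ≥3, re-treatment, prohibited therapy or drop-out, and with date-barred finishers censored at week 116.
   - *Single-visit PASI endpoints:* NRI in the cohort whose week-116 date allowed entry to the extension, with re-treated subjects kept as failures.
   - *Decliners:* show them both ways, as failures and as censored (or excluded), because week 116 was their planned end too.
   - *Barred for prohibited medication:* keep as failures.

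Define date-barred from the actual site implementation dates of Amendment 5. If these are unavailable, use a range of delays after the amendment date, for example 3 and 6 months. Leave out a delay of 0 months, because it would misclassify date-barred subjects as decliners.

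The cost is one derived flag and a few tables. Fewer subjects contribute after week 116, and the supplementary analysis assumes that the earliest enrolled subjects do not differ systematically from later ones.

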7. TREATMENT COMPLIANCE

Each administration of study drug performed at a study visit will be recorded in the subject's source documents, with the assistance of a staff member at the study site who will be supervising study drug administration at these visits. For any study drug administration performed by the subject outside of a study site, subjects will keep the syringe carton and return the empty carton to the study site at their next visit. The subject will record the corresponding date and time of the administration in the study drug application card. Study site personnel will utilize subject's documentation to ensure compliance and record at-home study drug administrations in the eCRF.

Week 0 can be done once all screening activities are completed, results are available, and the subject is eligible, but latest 4 weeks after screening visit (+ 7 calendar days). From weeks 4 through week 68 it is expected that all visits will occur within a range of ± 7 days. Any visits outside of these ranges should be discussed with the Sponsor. If a study visit occurs outside the specified visit window, the subject should then resume his or her normal dose schedule relative to the baseline visit (week 0) as soon as possible. Study visits in Study Part 3 should occur within ± 14 days of the scheduled study visit. Visits during the re-treatment period (study groups 2d and 3c) are also expected to occur within a range of ± 7 days. Any out-of-range visit should be documented in the subject's source notes and discussed with the sponsor.

Study-site personnel will maintain a log of all study drug administered. Drug supplies for each subject will be inventoried and accounted for. Information regarding study drug administrations that are administered outside of the scheduled windows or missed will be recorded. Subject charts and worksheets may be reviewed and compared with the data entries on the eCRF and IWRS to ensure accuracy. Although it is understood that treatment may be interrupted for many reasons, compliance with the treatment schedule is strongly encouraged.

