Subjects of group 2a and 2b with a PASI score <3 at week 68 enter Study Part 3 (in study groups **3a** and **3b**, respectively); they are withdrawn from the study medication and followed-up until week 220. Study visits of Study Part 3 are conducted every 12 weeks (ie, at weeks 80, 92, 104, 116, 128, 140, 152, 164, 176, 188, 200, and 212; \pm 14 days). In between the 12-weekly on-site visits, a telephone-visit 6 weeks (\pm 7 days) is done after each on-site visit (ie, telephone visits at weeks 74, 86, 98, 110, 122, 134, 146, 158, 170, 182, 194, and 206) to assess whether the subject notices a worsening of his/her psoriasis. If so, the subject must attend an on-site visit for efficacy assessment by the assessor as soon as possible but not later than 2 weeks after the phone call. For patients not starting re-treatment, the final visit takes place at week 220.

Re-treatment

Subjects losing control of disease, defined as PASI score >5 at any visit during Study Part 2 or 3 (ie, until week 220), enter the re-treatment-arms (**2d** or **3c**) with three guselkumab 100 mg administrations starting at that visit (= re-treatment-week 0, followed by administration at re-treatment-weeks 8 and 16).

If re-treatment is started at a visit which would usually not require all patient-reported outcomes needed at the first re-treatment visit, those patient-reported outcomes are obtained immediately after efficacy assessments (basis for re-treatment-decision) and prior to drug administration at that visit.

[figure not shown]
The final efficacy assessment for all subjects in the re-treatment arms takes place 24 weeks after loss of control, and study termination is 28 weeks after loss of control (final study visit/safety follow-up). At visit week 24 of the re-treatment, the investigator may continue actual treatment

with commercially available guselkumab (ie, not supplied by Sponsor) to maintain a q8w interval. Due to the half-life of guselkumab, it is recommended not to start a new therapy during safety follow-up period (ie, 12 weeks after last dose). If the investigator feels strongly that an additional therapy is needed, this should be discussed with the Sponsor before initiation of the new therapy.

Subjects with fluctuating disease (ie, PASI score 3 to 5) at the week 68 visit also get the opportunity to enter the re-treatment-arm (**3c**).

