Telephone visits scheduled at weeks 74, 86, 98, 110, 122, 134, 146, 158, 170, 182, 194, and 206, will not be re-assigned, as no endpoint data are assessed at these visits.

If there are site visits outside of the defined windows above, final decisions on the allocation of the actual visit to an earlier or later planned visit or whether the data will not be included in the analysis will be made during the Data Review or Dry Run Meeting.

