5.4. Major Secondary Endpoint(s) Analysis

Statistical analyses will be descriptive and exploratory only. They will be performed for the Intent-to-treat analysis set and, if requested, the Per-protocol analysis set.

Major secondary endpoints of this study in Study Part 3 are:

- Proportion of subjects with short (≤ 2 years) and longer (>2 years) disease duration who achieve an absolute PASI score of 0, ≤ 1 and <3 at weeks 116, 164, and 220, per study group
- Proportion of subjects who retain disease control (ie, absolute PASI score <3 at all visits) from week 68 through week 116, from week 68 through week 164, and from week 68 through week 220, for subjects with short (≤ 2 years) and longer (>2 years) disease duration per study group.

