6.2. Appendix 2 Changes to Protocol-Planned Analyses

No important changes from the planned analyses specified in the protocol and its amendments were applied.

However, the time point of analyses is changed slightly. While the CSP states that “interim analyses are planned after all subjects have completed their visit at week 116 (or at week 144 in case of subjects entering the re-treatment arm in week 116) and at week 164 (or at week 192 in case of subjects entering re-treatment arm in week 164). The final analysis will be performed after all subjects have completed their visit at week 220 (or at week 248 in case of subjects entering the re-treatment arm in week 220)”, it was decided to split the analyses of group 3a/3b subjects and the analyses of group 3c subjects (re-treatment phase). By this, the results for the week 116/164/220 analyses of study groups 3a and 3b will be available as soon as possible. A separate SAP will be written for the analysis of the re-treatment phase that will include – beneath the group 3c – also the analysis of study group 2d (subjects who entered the re-treatment phase already in study part 2).

In addition, some new analyses have been added to the evaluation; see section 5.6 for details.

The initial SAP, prepared before the Dry-run meeting for the first interim analysis (week 116), was updated several times during the course of the study:

- Changes introduced before the Week 116 analysis:
 - The windows for the week 28, 68, 116, 164 and week 220 visits are expanded.
 - For LOCF, the earliest visit used for carrying forward is the week 68 visit.
 - Statistical testing for binary endpoints is also performed for the OC analysis.
 - For binary endpoints, a modified OC analysis is done to exclude visits with PASI>5.
 - Subgroups are compared by statistical testing.
 - The analysis of adverse events excluded AEs starting on the day of the R0 visit.
- Change introduced before the Week 164 analysis:
 - Demographic data are displayed separately for each subgroup.
- Changes introduced before the Week 220 analysis:
 - The subgroups C to H are not evaluated for the analysis of PASI and DLQI response.
 - For the time-to-event endpoints, subgroups I to H are added.
 - All efficacy endpoints (PASI, DLQI, PSSD, BSA, and NAPPA scores and changes from baseline) by visit are presented only for visits with PASI < 5 (OC modified), with subgroups A and B.
 - PASI and DLQI response by visit are evaluated for NRI and OC modified.

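### Under non-responder imputation, one missed interior visit fails a patient on 'retain disease control' even when PASI is below 3 on both sides of the gap, and the share of true retainers lost this way rises with the length of follow-up.

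*SAP*

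**What the plan says.** All section numbers are those of the SAP for Study Part 3 (the drug withdrawal phase) unless another document is named.

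- **Endpoint.** Section 5.4 lists as a major secondary endpoint: "Proportion of subjects who retain disease control (ie, absolute PASI score <3 at all visits) from week 68 through week 116", with parallel versions through weeks 164 and 220.
- **Missing data.** Section 5.1.8: "Non-responder imputation for binary efficacy endpoints will be applied for subjects with missing data at any study visit". Neither 5.1.8 nor 5.4.3 has a separate rule for a gap between two observed visits.
- **Schedule.** Section 1.2: "Study visits of Study Part 3 are conducted every 12 weeks" (weeks 80 to 212), with a last visit at week 220.
- **Companion analysis.** Section 5.4.3 plans frequency tables "providing the number and percentage of subjects per study group (NRI and OC analysis"). Section 5.1.8 calls the observed-cases (OC) results descriptive only, but Appendix 2 (section 6.2) says: "Statistical testing for binary endpoints is also performed for the OC analysis".
- **Windows.** The protocol (section 7) says: "Study visits in Study Part 3 should occur within ± 14 days of the scheduled study visit". Table 2 of section 5.1.1 gives most interior Part 3 visits a window of 28 days either side of target. For visits outside every window, "final decisions on the allocation of the actual visit to an earlier or later planned visit or whether the data will not be included" is left to the Data Review or Dry Run Meeting.

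**The concern.** The endpoint is a composite over visits, and the imputation rule acts on each visit. A single empty visit is therefore enough to turn a patient with documented control before and after it into a failure, and that failure carries forward to every later horizon. NRI is usually defended because drop-out may reflect loss of efficacy. That argument is weak for a patient who comes back with PASI still below 3.

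The longer a patient stays in drug-free control, the more visits must all be present. Part of the fall in the retention rate between weeks 116, 164 and 220 could then reflect attendance and not disease. The endpoint also serves the secondary objective of comparing short and longer disease duration. A rule that removes true retainers shrinks any true difference in proportions, even when attendance is equal in the two groups.

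Missed and delayed visits are foreseen. Protocol Attachment 6 expects them during the pandemic and promises additional analyses in the SAP(s), but the Part 3 SAP contains no such rule.

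**Working it through.** **No plan figure to reproduce.** The documents state neither an expected retention rate nor a missed-visit rate for Part 3. The miss rate m below is an assumption.

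**Step 1: interior visits at risk (section 1.2).** These are the on-site visits after week 68 and before the final visit of each horizon.

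- Week 116: 80, 92, 104, so k = 3.
- Week 164: those three plus 116, 128, 140, 152, so k = 7.
- Week 220: those seven plus 164, 176, 188, 200, 212, so k = 12.

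**Step 2: chance that a true retainer is scored as a failure.** With independent misses this is 1 − (1 − m)^k.

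| m (assumed) | Week 116 | Week 164 | Week 220 |
|---|---|---|---|
| 1% | 1 − 0.99^3 = 3.0% | 1 − 0.99^7 = 6.8% | 1 − 0.99^12 = 11.4% |
| 2% | 1 − 0.98^3 = 5.9% | 1 − 0.98^7 = 13.2% | 1 − 0.98^12 = 21.5% |
| 5% | 1 − 0.95^3 = 14.3% | 1 − 0.95^7 = 30.2% | 1 − 0.95^12 = 46.0% |

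Independence gives the larger figure. If misses cluster in the same patients, fewer patients have at least one miss at the same average rate.

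**Step 3: patients.** The overall safety SAP (sections 4.4 and 4.5) reports 273 patients entering withdrawal, of whom 227 were re-treated after PASI above 5. At most 273 − 227 = 46 (16.8%) can have kept control to week 220. The largest possible loss at week 220 is then:

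- m = 1%: 46 × 0.114 = about 5 patients, or 1.9 points of 273.
- m = 2%: 46 × 0.215 = about 10 patients, or 3.6 points.
- m = 5%: 46 × 0.460 = about 21 patients, or 7.7 points.

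**Step 4: does the loss in percentage points grow?** It equals S × [1 − (1 − m)^k], where S is the true share in control. S falls while the bracket rises. As an illustration, take an exponential curve through the week-220 ceiling, so that S = (46/273)^((week − 68)/152). This gives S = 57.0%, 32.5% and 16.8%. At m = 2% the loss is 3.4, 4.3 and 3.6 points, so it rises and then falls.

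**Step 5: effect on a group difference.** With the same m in both disease-duration groups, a true 20-point difference becomes 20 × 0.98^k = 18.8, 17.4 and 15.7 points at m = 2%. The relative risk is unchanged.

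**Step 6: windows (Table 2).** Target days follow 7 × week + 1; for week 92 this is 645. Every visit within the protocol's 14 days falls inside its own window. Seven gaps remain, each of 27 days: days 590–616, 674–700, 926–952, 1010–1036, 1262–1288, 1346–1372 and 1430–1456. Only a visit more than 28 days off target lands in one. Separately, a week 104 visit 29 or more days late (day 729 + 29 = 758) falls in the week 116 window and leaves week 104 empty.

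**The case against.** The case for leaving the plan alone has real strength.

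- **NRI is protocol-specified, and Part 3 is exploratory.** Protocol sections 11.3 and 11.11 apply NRI to the major secondary endpoints, and an unseen visit cannot confirm control at all visits. This stands as a reason to keep strict NRI. It does not settle the interior gap, because section 11.11 describes discontinuation and failure to return at the endpoint visit.
- **Other analyses are not harmed by a gap.** OC is planned for the same endpoint. Time to loss of disease control does not replace missing data. Response at weeks 116, 164 and 220 does not depend on interior visits. This stands in part. However, OC keeps data after prohibited therapy and imputes nothing for drop-outs, and its derivation with an interior gap is not stated. The modified OC analysis disregards patients with PASI above 5, who are true failures. Time to loss of control uses PASI above 5, not retention below 3.
- **The size is assumed.** This stands. Neither the miss rate nor independence comes from the documents.
- **The window gaps are remote.** This largely stands. No protocol-compliant visit reaches one, and the meeting may still allocate the visit.

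A reader might infer more than the documents support:

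- That the artefact grows each year in absolute terms. Step 4 shows that it need not.
- That late visits are lost automatically. Section 5.1.1 allows them to be allocated.
- That the disease-duration comparison is biased by unequal attendance. Nothing in the documents shows unequal attendance.

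**Conclusion.** The point holds for the NRI analysis of this one endpoint. As written, a single missing interior visit is a failure whatever was observed on either side, and no planned analysis of the endpoint fully repairs this.

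The share of true retainers lost rises across weeks 116, 164 and 220 for any non-zero miss rate that is constant and independent across visits. It is 5.9%, 13.2% and 21.5% at an assumed 2%, and 3.0%, 6.8% and 11.4% at 1%. In patients, the week-220 loss is at most about 10 of 46 at 2% and about 5 at 1%, and less if misses cluster.

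The documents do not support the view that strict NRI is invalid or should be withdrawn. It follows the protocol, and the overall safety SAP (section 1) reports the Part 3 analyses as already performed. Replacing the rule now would be post hoc. The window gaps are a secondary matter. They count because visits falling in them are settled case by case, after the sponsor was unblinded at the week 68 database lock (protocol section 5).

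**What to change.** 1. **Sections 5.1.8 and 5.4.3.** Add a defined analysis of 'retain disease control' beside strict NRI, labelled supplementary if outputs already exist. In it, a missing interior visit is not a failure when the nearest observed PASI values before and after are both below 3, with no re-treatment and no prohibited therapy between them. Keep NRI for drop-out, for prohibited therapy and for a missing final visit.
2. **Reporting.** Give the number of patients who fail strict NRI only through a gap, at each horizon, by study group and by disease duration. This replaces the assumed miss rate with an observed count.
3. **OC.** State how the all-visits composite is derived when an interior visit is missing, and reconcile section 5.1.8 (descriptive only) with Appendix 2 (tested).
4. **Table 2.** Make the interior Part 3 windows contiguous, closing the seven 27-day gaps, so that an attended visit far off target is assigned by rule. This alone does not rescue a very late week 104 visit; item 1 does.

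The cost is one derivation, one extra table and some SAP wording, with no change to patient management. The downside is that a brief, unseen PASI of 3 or more at a missed visit would not be counted. The strict NRI result bounds this, because it counts every such gap as a failure.
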